11.2.2 Adverse Events of Special Interest

The following AEs of special interest will be summarized by number and percentage of subjects experiencing an AE of interest. The AEs of interest will be summarized and presented using primary MedDRA system organ classes (SOCs) and preferred terms (PTs) for the following AE categories:

- Any Infections AE

- Any Serious Infection AE
- Any Legionella Infection AE
- Any Diverticulitis AE
- Any Opportunistic Infection AE (Excluding Oral Candidiasis and TB)
- Any Oral Candidiasis
- Any Tuberculosis AE
- Any Active Tuberculosis
- Any Latent Tuberculosis
- Any Parasitic Infection AE
- Any Reactivation of Hepatitis B
- Any Progressive Multifocal Leukoencephalopathy (PML) AE
- Any Malignancy AE
- Any Lymphoma AE
- Any Hepatosplenic T-Cell Lymphoma AE (HSTCL)
- Any Non-Melanoma Skin Cancer (NMSC) AE
- Any Melanoma AE
- Any Leukemia AE
- Any Other Malignant AE (Excluding NMSC, Melanoma, Lymphoma, HSTCL, and Leukemia)
- Any Allergic Reaction (Including Angioedema/Anaphylaxis)
- Any Lupus-Like Reactions and Systemic Lupus Erythematosus
- Any Vasculitis AE
- Any Cutaneous Vasculitis AE
- Any Non-Cutaneous Vasculitis AE
- Any Sarcoidosis AE
- Any Autoimmune Hepatitis
- Any Myocardial Infarction Related AE
- Any Cerebrovascular Accident Related AE
- Any Congestive Heart Failure Related AE

- Any Pulmonary Embolism Related AE
- Any Interstitial Lung Disease AE
- Any Intestinal Perforation AE
- Any Pancreatitis AE
- Any Stevens-Johnson Syndrome AE
- Any Erythema Multiforme Related AE
- Any Worsening/New Onset of Psoriasis
- Any Demyelinating Disorder
- Any Amyotrophic Lateral Sclerosis AE
- Any Reversible Posterior Leukoencephalopathy Syndrome (RPLS) AE
- Any Hematologic Disorders AE (Including Pancytopenia)
- Any Liver Failure and Other Liver Event AE
- Any Humira Administration Related Medication Errors AE
- Any Injection Site Reaction AE
- Any Intestinal Stricture
- Any AE Leading to Death
- Any AE Leading to Discontinuation of Study Drug.
- Any Deaths

Additional AEs may be considered for tabulation/summary based on recommendations from Clinical and Safety as deemed appropriate.

11.3 Analysis of Laboratory Data

All laboratory data collected after first dose of maintenance study drug will be included in this analysis.

Changes from Baseline in continuous laboratory parameters will be summarized by n, mean, standard deviation, minimum value, median, and maximum value for each treatment group.

Cross (Shift) tables from Baseline to the minimum, maximum, and final value according to the normal range will be provided for each hematology, clinical chemistry parameter and urinalysis parameter except for the microscopic examination.

For selected laboratory parameter with Common Toxicity Criteria (CTC) a listing of all subjects with any laboratory determinations meeting CTC Version 3.0 of Grade ≥ 3 will be provided. For each of these subjects, the whole course of the parameter will be listed. For subjects with laboratory values with CTC ≥ 3 , all of the laboratory parameters for those subjects will be listed.

The laboratory data using Abbott platform will be used for this analysis. If the data measured using Abbott platform are not available, the Abbott equivalent (the values measured using Roche platform that were converted to Abbott equivalent) will be used.

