**Safety:**

Adverse events (AEs), laboratory data and vital signs are the primary safety parameters in this study. All safety comparisons will be performed between treatment groups using the safety set.

Treatment-emergent AEs are defined as events that begin or worsen either on or after the first dose of the study drug and within 70 days after the last dose of the study drug for subjects who do not participate in the OLE or until first dose of study drug in the OLE study if the subject is a study completer and is enrolled in the OLE. Treatment-emergent AEs will be summarized separately for: a) Baseline to Week 12; b) Week 12 to Week 56; c) Baseline to Week 56 (overall study duration). An overview of treatment-emergent AEs, including AEs of special interest, adverse events leading to death and adverse events leading to premature discontinuation (see details in the SAP), AEs by Medical Dictionary for Drug Regulatory Activities (MedDRA version 20.1 or later) preferred term and system organ class, AEs by maximum relationship to study drug, and AEs by maximum severity will be summarized by number and percentage.

Changes in laboratory data will be described using statistical characteristics and compared between-treatment groups will be performed using a one-way Analysis of Variance (ANOVA). In addition, shift tables and listings will be provided for abnormal values, whereby the normal range of the analyzing laboratory will be used. Vital signs will be analyzed similarly.

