### **8.1.5 Statistical Analyses of Safety**

Adverse events (AEs), laboratory data and vital signs are the primary safety parameters in this study. All safety comparisons will be performed for both induction and maintenance periods between treatment groups using the safety analysis set.

Treatment-emergent AEs are defined as events that begin or worsen either on or after the first dose of the study drug and within 70 days after the last dose of the study drug for subjects who do not participate in the OLE or until first dose of study drug in the OLE study if the subject is a completer and is enrolled in the OLE.

Treatment-emergent AEs will be summarized separately for: a) Baseline to Week 12; b) Week 12 to Week 56; c) Baseline to Week 56 (overall study duration). An overview of treatment-emergent AEs, including AEs of special interest such as adverse events leading to death and adverse events leading to premature discontinuation (see details in the SAP), AEs by Medical Dictionary for Drug Regulatory Activities (MedDRA version 20.1 or later) preferred term and system organ class, AEs by maximum relationship to study drug, and AEs by maximum severity will be summarized by number and percentage.

Changes in laboratory data will be described using statistical characteristics and compared between treatment groups will be performed using a one-way Analysis of Variance (ANOVA). In addition, shift tables and listings will be provided for abnormal values, whereby the normal range of the analyzing laboratory will be used. Vital signs will be analyzed similarly.

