11.4 Analysis of Vital Signs and Weight

All vital signs and weight data collected after first dose of maintenance study drug will be included in this analysis.

The following vital signs are measured at every visit during the study.

- Body Weight (kg)
- Blood Pressure (Systolic/Diastolic) (mmHg)
- Pulse (bpm)
- Respiratory Rate (RPM)
- Temperature (°C)

Changes from Baseline in vital sign values will be summarized by n, mean, standard deviation, minimum value, median, and maximum value for each treatment group.

The number and percentage of subjects meeting the criteria for potentially clinically significant (PCS) vital sign values will also be summarized.

The criteria for potentially clinically significant vital sign findings are presented in [Table 8](#).

Table 8. Criteria for Potentially Clinically Significant Vital Sign Findings

Vital Sign	Category	Criteria for Potential Clinically Significant Vital Signs
Systolic blood pressure	Low	Value \leq 90 mmHg and/or decrease \geq 20 mmHg from Baseline
	High	Value \geq 180 mmHg and/or increase \geq 20 mmHg from Baseline
Diastolic blood pressure	Low	Value \leq 50 mmHg and/or decrease \geq 15 mmHg from Baseline
	High	Value \geq 105 mmHg and/or increase \geq 15 mmHg from Baseline
Pulse	Low	Value \leq 50 bpm and/or decrease \geq 15 mmHg from Baseline
	High	Value \geq 120 mmHg and/or increase \geq 15 mmHg from Baseline

Vital sign results meeting the criteria for PCS findings will be identified in a listing.

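### The protocol compares laboratory and vital-sign changes between arms by one-way ANOVA; both SAPs plan only per-arm descriptive statistics and do not declare the difference

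*SAP*

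**What the plan says.** **Protocol.** Section 8.1.5 names adverse events, laboratory data and vital signs as the primary safety parameters. On scope it says: "All safety comparisons will be performed for both induction and maintenance periods between treatment groups using the safety analysis set". Laboratory changes are to be described and "compared between treatment groups will be performed using a one-way Analysis of Variance (ANOVA"). It then adds: "Vital signs will be analyzed similarly". The Safety part of the synopsis gives the same ANOVA rule.

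**SAPs.** Section 11.3 has the same sentence in the Induction and the Maintenance SAP: "Changes from Baseline in continuous laboratory parameters will be summarized by n, mean, standard deviation, minimum value, median, and maximum value", in each arm. Section 11.4 has the matching sentence for vital signs: "Changes from Baseline in vital sign values will be summarized by n, mean, standard deviation, minimum value, median, and maximum value for each treatment group". None of these four sections names a test, a between-arm difference or a confidence interval for the changes.

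**Change logs.** Section 12.1 of the Induction SAP reports no differences from the latest protocol. Section 12.1 of the Maintenance SAP lists only changes to efficacy endpoints.

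**The concern.** Both SAPs state that they elaborate the methods of Protocol Amendment 6. On this point they leave out a comparison that the amendment still contains, and the reader is not told. A programmer who works from the SAPs will produce side-by-side columns and nothing that compares them. A reader of Induction SAP 12.1 will believe that the protocol was followed.

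The stakes are clearest in induction, where the study asks whether a higher dose is worthwhile. From the doses in protocol 5.5.1, the higher arm receives 4 × 160 = 640 mg through Week 3 and the standard arm 160 + 80 = 240 mg. Whether laboratory values or vital signs move differently between these arms is an ordinary safety question, and the protocol set out to answer it.

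**Working it through.** **1. Is the ANOVA current text?** Yes. The list of changes for Amendment 6 shows that section 8.1.5 was edited: the Fisher test for adverse events by preferred term was deleted and the MedDRA version updated. The ANOVA for laboratory data remains in the current 8.1.5 and in the current synopsis.

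**2. The texts side by side.**

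| Item | Protocol 8.1.5 | Induction SAP | Maintenance SAP |
|---|---|---|---|
| Laboratory change | Described, and compared by one-way ANOVA | 11.3: per-arm n, mean, SD, minimum, median, maximum | 11.3: the same |
| Vital-sign change | Handled like laboratory data | 11.4: per-arm statistics only | 11.4: per-arm statistics only |
| Declared as a change | – | 12.1: no differences declared | 12.1: efficacy endpoints only |

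**3. What between-arm information remains planned?**
- Frequencies and percentages for the potential Hy's law criteria, by treatment group as treated (11.3.2).
- Counts of potentially clinically significant vital signs (11.4), by treatment received under 11.1.
- Laboratory shift tables, listings of Grade 3 or higher values, and adverse events of special interest that include hematologic and liver events.

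**4. Can the omitted comparison be rebuilt?** With two arms, yes, from the statistics that the SAPs do report:
- d = m₁ − m₂
- s² = [(n₁ − 1)s₁² + (n₂ − 1)s₂²] / (n₁ + n₂ − 2)
- SE = s√(1/n₁ + 1/n₂)
- F = (d/SE)²

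On simulated data with arms of 300 and 200, the ANOVA on the raw values gave F = 19.533, and the square of t from n, mean and SD alone was also 19.533. A baseline-adjusted estimate cannot be rebuilt this way, because it also needs the correlation between baseline and follow-up.

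**5. How precise would the induction comparison be?** The inputs are the planned 300 and 200 subjects (protocol 8.2), with no missing data assumed. The documents give no SDs for these parameters, so results are in units of the SD of change.
- SE = √(1/300 + 1/200) = 0.091 SD
- 95% CI half-width = 1.96 × 0.0913 = 0.18 SD
- Difference with 80% power, two-sided 0.05 = (1.96 + 0.84) × 0.0913 ≈ 0.26 SD
- Power at 0.1, 0.2 and 0.3 SD: 19%, 59% and 91%

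Maintenance arm sizes are not stated, so no figure is given for that period.

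**6. What would baseline adjustment add?** If baseline and follow-up have equal variance and correlation r, the variance from ANCOVA relative to ANOVA on change is (1 − r²) / [2(1 − r)] = (1 + r)/2. For assumed r of 0.4, 0.6 and 0.8 this is 0.70, 0.80 and 0.90, or 30%, 20% and 10% less variance. This bears on the choice of method for the fix. It does not measure the omission.

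**7. Which baseline applies in the Maintenance SAP?** Section 6.0 defines an Induction Baseline and a Maintenance Baseline. The unqualified baseline value is defined under the Induction heading, and section 11.3.1 uses the Induction Baseline for liver shifts. Sections 11.3 and 11.4, including Table 8, do not say which is meant. The natural reading is the Induction Baseline, but it has to be inferred.

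**The case against.** **Silence may not mean exclusion.** The SAPs elaborate the protocol, and where they intend no testing they say so: in 7.2, 7.3 and 11.3.1 of both. The general laboratory and vital-sign sections carry no such statement, so the ANOVA could be thought to apply by reference. This is weak. Section 7.1 of both SAPs spells out an analysis of variance, with the SAS procedure, for baseline characteristics. Where ANOVA was intended it was written down.

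**Little is lost.** This largely stands. A reader might infer that a modest dose-related shift could not be judged from the planned output. The documents do not support that: steps 3 and 4 show that by-arm frequencies remain and that the unadjusted difference and its interval can be derived. What is missing is the planned comparison, not the information behind it.

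**The protocol promised less than an estimate.** This stands too. A reader might take 8.1.5 to require a difference with a confidence interval for every parameter. It asks only for a comparison by ANOVA; the interval is an improvement proposed here.

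**Multiplicity.** Protocol Table 4 lists 27 hematology and chemistry parameters. With the four post-baseline windows in Table 4 of the Induction SAP that makes 27 × 4 = 108 comparisons, and 0.05 × 108 ≈ 5 would fall below 0.05 by chance if there were no effect. This is a reason to present intervals as descriptive. It does not justify dropping the comparison without saying so.

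**Maintenance is different.** The 640 mg against 240 mg contrast belongs to induction. The maintenance analyses are exploratory and have no sample-size calculation, so the dose argument does not carry over. The mismatch between documents does, because 8.1.5 covers both periods.

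**Conclusion.** The protocol and both SAPs disagree, and the disagreement is undeclared. It covers laboratory and vital-sign changes in both periods. As the SAPs stand, no between-arm comparison of these changes is planned, and the statement in Induction SAP 12.1 that nothing differs from the protocol is incorrect on this point.

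Severity is low to moderate. The co-primary endpoints are untouched, by-arm frequencies of notable values remain, and the unadjusted comparison is recoverable. The finding rests on reading the texts together and on no numerical assumption. The 0.18 SD half-width assumes 300 and 200 subjects with complete data. The 10–30% variance gain assumes r between 0.4 and 0.8 and equal variances, and is not a measure of the omission. The baseline wording in the Maintenance SAP is a lesser point of clarity.

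**What to change.** - In sections 11.3 and 11.4 of both SAPs, add the between-arm difference in mean change with a 95% CI, labelled descriptive and unadjusted for multiplicity. Preferably take it from a model with treatment and the baseline value of that parameter.
- In 11.3, 11.4 and Table 8 of the Maintenance SAP, state which baseline applies. Both defined baselines are available; the text needs to name one.
- In section 12.1 of each SAP, record any move from the protocol's one-way ANOVA.
- If the sponsor prefers to drop the comparison, record that in both 12.1 sections and align protocol 8.1.5 and the synopsis.

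The cost is a few lines of text and some extra columns in tables already planned; no new data are needed. The downside is a large number of unadjusted intervals, which the descriptive label addresses.

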11.3.1 Assessment of Shifts from Induction Baseline in Liver-Specific Laboratory Variables

Induction Baseline and post-maintenance baseline livers-specific laboratory will be categorized as follows:

- < 1.5 times the upper limit of the reference range
- ≥ 1.5 to < 3 the upper limit of the reference range
- ≥ 3 to < 5 the upper limit of the reference range
- ≥ 5 to < 8 the upper limit of the reference range
- ≥ 8 the upper limit of the reference range

For each variable, shift tables will be generated as deemed appropriate:

- Category of the induction baseline value versus category of the final value,
- Category of the induction baseline value versus post-maintenance baseline high/low category

Note that the maximum category is used, rather than the category of the maximum values. The two may be different due to variation in the reference range.

No statistical tests will be performed for this analysis.

A listing of potentially clinically significant liver function laboratory values will be provided. The listing includes all subjects who met any of the following 4 criteria:

ALT $\geq 2.5 \times$ ULN, or

AST $\geq 2.5 \times$ ULN, or

Alkaline Phosphatase $\geq 2.5 \times$ ULN, or

Total Bilirubin $\geq 1.5 \times$ ULN.

11.3.2 Hy's Law Cases

According to FDA's Guidance for Industry "Drug-Induced Liver Injury: Premarketing clinical evaluation" (July 2009), when aminotransferase (AT) abnormalities indicating hepatocellular injury are accompanied by evidence of impaired hepatic function (bilirubin elevation $> 2 \times$ ULN), in the absence of evidence of biliary obstruction (i.e., significant elevation of ALP) or some other explanation of the injury (e.g., viral hepatitis, alcohol hepatitis), the combined finding (i.e., Hy's Law cases) represents a signal of a potential for the drug to cause severe DILI.

For the purpose of assessing for potential Hy's law cases, the frequencies and percentages of subjects with post baseline liver specific function test values that meet the following criteria of potential clinical interest will be summarized by "as treated" treatment group:

- ALT $\geq 3 \times$ ULN
- ALT $\geq 5 \times$ ULN
- ALT $\geq 10 \times$ ULN
- ALT $\geq 20 \times$ ULN

- $AST \geq 3 \times ULN$
- $AST \geq 5 \times ULN$
- $AST \geq 10 \times ULN$
- $AST \geq 20 \times ULN$
- $TBL \geq 2 \times ULN$
- Alkaline phosphatase $\geq 1.5 \times ULN$
- ALT and/or AST $\geq 3 \times ULN$ and concurrent TBL $\geq 1.5 \times ULN$
- ALT and/or AST $\geq 3 \times ULN$ and concurrent TBL $\geq 2 \times ULN$

11.4 Analysis of Vital Signs and Weight

All vital signs and weight data collected after first dose of maintenance study drug will be included in this analysis.

The following vital signs are measured at every visit during the study.

- Body Weight (kg)
- Blood Pressure (Systolic/Diastolic) (mmHg)
- Pulse (bpm)
- Respiratory Rate (RPM)
- Temperature (°C)

Changes from Baseline in vital sign values will be summarized by n, mean, standard deviation, minimum value, median, and maximum value for each treatment group.

The number and percentage of subjects meeting the criteria for potentially clinically significant (PCS) vital sign values will also be summarized.

The criteria for potentially clinically significant vital sign findings are presented in [Table 8](#).

Table 8. Criteria for Potentially Clinically Significant Vital Sign Findings

Vital Sign	Category	Criteria for Potential Clinically Significant Vital Signs
Systolic blood pressure	Low	Value \leq 90 mmHg and/or decrease \geq 20 mmHg from Baseline
	High	Value \geq 180 mmHg and/or increase \geq 20 mmHg from Baseline
Diastolic blood pressure	Low	Value \leq 50 mmHg and/or decrease \geq 15 mmHg from Baseline
	High	Value \geq 105 mmHg and/or increase \geq 15 mmHg from Baseline
Pulse	Low	Value \leq 50 bpm and/or decrease \geq 15 mmHg from Baseline
	High	Value \geq 120 mmHg and/or increase \geq 15 mmHg from Baseline

Vital sign results meeting the criteria for PCS findings will be identified in a listing.

12.0 Summary of Changes

12.1 Summary of Changes Between the Latest Version of Protocol and the Current SAP

Under Section 10.2 Efficacy Analyses, there was a typo for the endpoint "Proportion of subjects with CDAI < 150 at Week 4 and SES-CD \leq 4 and at least 2 point reduction versus baseline and no subscore greater than 1 in any individual variable at Week 56." It should be Week 56 for CDAI < 150, not Week 4. The endpoint has been updated in the SAP to "Proportion of subjects with CDAI < 150 at Week 56 and SES-CD \leq 4 and at least 2 point reduction versus baseline and no subscore greater than 1 in any individual variable at Week 56."

Under Section 10.2 Efficacy Analyses, the following explanatory endpoints are added:

- Proportion of subjects who achieve endoscopic remission (SES-CD \leq 4 and at least a 2 point reduction versus Induction Baseline and no subscore greater than 1 in any individual variable) at Week 56 among subjects with endoscopic response at Week 12.
- Proportion of subjects with endoscopic response, and \geq 50% decrease from Induction Baseline in hs-CRP or fecal calprotectin at Week 56.
- Proportion of subjects with endoscopic remission, and \geq 50% decrease from Induction Baseline in hs-CRP or fecal calprotectin at Week 56.

- Proportion of subjects with clinical remission, and $\geq 50\%$ decrease from Induction Baseline in hs-CRP or fecal calprotectin at Week 56.

12.2 Summary of Changes Between the Previous Version and the Current Version of the SAP

This is the first version of the SAP.

3.0 Introduction

This statistical analysis plan (SAP) describes the statistical analysis to be completed by the AbbVie Global Statistics Department for study Protocol M14-115 Amendment 6. It provides details to further elaborate statistical methods as outlined in the protocol and describes analysis conventions to guide the statistical programming work.

This is the fourth version of the SAP for the 12-Week Double-Blind Induction Study of Protocol M14-115.

This analysis plan describes the primary and secondary efficacy analyses as well as the safety analysis for the 12-week double-blind induction study.

This document describes the analysis of data except pharmacokinetic, microbiota metagenomic, pharmacogenetic and serologic data which will be analyzed separately. It takes into account ICH Guidelines E3 and E9.

Unless noted otherwise, all analyses will be performed using SAS version 9.4 or later (SAS Institute Inc., Cary, NC 27513) under the UNIX operating system.

4.0 Study Objectives, Design and Procedures

4.1 Objectives

The primary objective of this study is to assess the efficacy and safety of two adalimumab induction regimens in achieving clinical remission (CDAI < 150) at Week 4 and endoscopic response defined as decrease in SES-CD > 50% from Baseline (or for a Baseline SES-CD of 4, at least a 2 point reduction from Baseline) at Week 12, in subjects with moderately to severely active Crohn's disease and evidence of mucosal ulceration at Baseline.

Additional objectives include:

- Assessing the efficacy and safety of two adalimumab induction regimens in reducing signs and symptoms of Crohn's disease at Week 12.
- Assessing the efficacy and safety of two adalimumab maintenance regimens in reducing signs and symptoms of Crohn's disease at Week 56.
- Assessing pharmacokinetics (PK) and immunogenicity of two adalimumab induction regimens following subcutaneous (SC) administration.

